1. OBJECTIVES

This project will be subdivided into three sections:

Part I. Comparison of the ESM vs. SR-BDs and other retrospective questionnaires in the assessment of urological complaints in OAB such as urgency.

Part II. Validation of new patient-reported outcome measure, based on the Experience Sampling Method, which will be used in the assessment of urological symptoms in patients with overactive bladder syndrome.

Part I – Comparison of assessment methods

Primary aim: To compare the ESM to SR-BDs and other retrospective questionnaires in the assessment of urological complaints in OAB.

Objectives:

1. To compare the ESM to SR-BDs and other retrospective questionnaires in the assessment of urological complaints in OAB.

Hypothesis: The ESM is more accurate in the assessment of urological complaints in OAB compared to the current use of SR-BDs and other retrospective questionnaires (like the OAB-q). We hypothesize to find good correlations between ESM scores (i.e. the newly developed ePRO) and 'concurrent' instruments (i.e. conventional retrospective questionnaires), since we purport to measure the same constructs with both methods. However, ESM measures real-time symptoms whereas our conventional questionnaires measure retrospectively. Therefore, we do not expect to find perfect correlation coefficients, i.e. >0.8. Correlation coefficients between 0.4 and 0.8 are considered appropriate. Correlation coefficients lower than 0.4 reflect very weak or no correlation between the methods, which probably means that we are measuring some other construct with our new ePRO than is measured with the conventional method (current 'gold standard'). On the contrary, correlation coefficients higher than 0.8 reflect very strong correlations, meaning that we are more or less measuring exactly the same construct. In this case, there is no rational for replacing the conventional methods by the new (more intensive) method. For each correlation coefficient its significance will be checked as well.

Furthermore it is expected that the mean urgency scores from the ESM will be significantly lower when compared to the urgency scores from the SR-BDs and retrospective questionnaires.

Additionally it is expected that in the SR-BDs the daily peak of urgency scores is reported rather than the average level of urgency over the day.

Part II - Validation

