4.2.2 Tool development

To apply ESM as a symptom assessment method in this study, an application suitable for smartphones has been developed. This application runs the previously selected set of items, as described in section 5.2.1.1. 'PROM development'.

The application can be downloaded freely on the personal smartphone of each participating subject. Once the application is downloaded and activated, it will work both online and offline to ensure that no assessments will be missed when not connected to the Internet. In online situations the answers will be directly and automatically sent to the general database; when offline the answers will be temporary stored at the smartphone and will be sent to the database as soon as an Internet connection is available. Encryption of data to assure on patient's privacy is described in detail in section 9.1 'Handling and storage of data and documents'.

Questions in the application will be designed in a hierarchical order, *i.e.* if the patient has no symptoms at that particular moment, there is no rationale for assessing triggers and therefore these questions will be automatically set to a default of "no" or "none". Further, if patients find an auditory signal

disturbing during their daily activities, they will be able to choose a vibration signal instead.

- 4.2.3 Retrospective symptom assessment conventional questionnaires Apart from ESM, participants will be instructed to complete a SR-BD during last 3 consecutive days of filling out the ESM (see 'F2. ESM_sensationrelated bladder diary_Versie 1.0 (11.08.2017)'). The SR-BD has to be filled out after each micturition. This is a voiding diary where people fill out at what time they had to void, how high the voided volume was and how high the urgency and perception of bladder fullness was what they experienced. Furthermore they have to fill out if and how much urine loss they had. Furthermore, participants will be instructed to complete additional (singletime) retrospective questionnaires, at the end of the test period of 7 days:
 - Baseline questionnaire for demographic characteristics (see F1.
 'ESM_Algemene Vragenlijst_Versie 1.0 (11.08.2017)').

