 - Sensation-related bladder diaries (see 'F2. ESM_sensation-related bladder diary_Versie 1.0 (11.08.2017)'). Besides urinary frequency and voided volume, these diaries also include the degree of urge and the perception of bladder fullness during each void. It has been recommended that evaluation of bladder sensations during daily activities is the most representative. ⁴⁸⁻⁵⁰ Sensation-related bladder diaries (SR-BDs) are a non-invasive tool that is used to evaluate these bladder sensations in daily life.
 - Overactive Bladder Questionnaire (OAB-q) (see F1. 'ESM_OABq_Versie1.0 (2016.10.17)'). 33-item questionnaire on LUTS and Health-related quality of life (HRQL) items.⁵¹
 - 3 Incontinence Questionnaire (3IQ) (see 'F1. ESM_3IQ_Versie 1.0 (11.08.2017)')⁵²
 - Female participants only :
 - International Consultation on Incontinence Modular Questionnaire – Female LUTS (see F1. 'ESM_ICIQFLUTS_Versie 1.0 (11.08.2017)').13-item questionnaire on lower urinary tract symptoms ^{53,54}.
 - Vragenlijst Werkgroep Bekkenbodem NVOG (see 'F1. ESM_VragenlijstNVOG_Versie 1.0 (11.08.2017)'). 47-short item questionnaire on pelvic symptoms.

- Male participants only:
 - International Consultation on Incontinence Modular Questionnaire – Male LUTS (see 'F1. ESM_ICIQMLUTS_Versie 1.0 (11.08.2017)').13-item questionnaire on lower urinary tract symptoms ^{53,54}.
 - International Prostate Symptom Score (see 'F1. ESM_IPSS_Versie 1.0 (11.08.2017)'). 7 item questionnaire on LUTS and 1 item questionnaire on Quality of Life⁵⁵.
 - International Index of Erectile Functions 5 (IIEF-5) (see 'F1. ESM_IIEF5_Versie 1.0 (11.08.2017). 5-item questionnaire to screen for erectile dysfunction. ⁵⁶
- Hospital Anxiety and Depression Scale (HADS) ((see 'F1. ESM_HADS_Versie 1.0 (11.08.2017)').⁵⁷
- Short Form-36 (SF-36) (see F1. ESM_SF36_Versie 1.0 (11.08.2017)'). Self-survey after general quality of life (not disease-specific)⁵⁸

Figure 2: Questionnaire timeline.

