6. STATISTICAL ANALYSIS

Part I – Comparison of the ESM to SR-BDs and other retrospective questionnaires

In case of incomplete ESM data, we will not use imputation techniques as these techniques have similar assumptions on the mechanisms of missing data as the statistical model described in the remaining text.

Experience Sampling Methods produce complex multilevel data structures, and analysis techniques need to take the variation between subjects and repeated measures within subjects into account. Associations between urological symptom scores of the SR-BD and corresponding ESM scores will be tested using linear mixed-effects models, with a random intercept to account for clustering of measurements within patients, and an autoregressive (AR1) covariate structure to account for correlations of measurements over time. Currently the SR-BD can be seen as the standard method and will therefore be used as dependent variable in the analysis. For each participant, ESM day-mean scores of individual symptoms will be used as predictor, to test whether average symptom scores of the day reflect the day-mean SR-BD scores.

To quantify the difference of scores between the two methods, ESM data will be subtracted from corresponding day-mean SR-BD scores, resulting in a delta score, which will be statistically tested using the same multilevel analysis, adjusting for repeated measures. In like manner, the differences between the mean SR-BD scores and ESM maximum scores of the day will be tested.

To investigate if certain patient characteristics lead to a different retrospective perception of urgency, possible predictors of a larger delta-score (i.e. the differences in urgency reporting between ESM day-mean scores and the day-mean SR-BD scores) will be tested: i.e. gender, age, presence of comorbid panic disorder and psychological symptoms (HADS).

Part II Validation

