6.1 Primary study parameter

Data used for analysis will comprise patient-reported scores from ESM, paper SR-BDs and single-time paper symptom questionnaires. The PROM will be psychometrically evaluated with regard to validity and reliability. These parameters will characterize the ESM measure and allow insight into the potential role of this method in clinical practice. Validity and reliability will be assessed according to following components ^{29,62,63}:

- Content validity reflects the extent to which the instrument as a whole measures all the relevant aspects that are indicative to the specific condition and population. This can be determined by taking into account evidence from qualitative studies, performing cognitive interviews to evaluate patients' understanding with the instrument and by taking into account experts' opinions ^{62,63}. In this study, content validity is assured by basing ESM items on theoretical constructs from the literature as well as by performing patient focus groups and expert meetings.
- Concurrent validity reflects the correlation between a new test and an existing test that purport to measure the same construct. ESM scores will be correlated with scores of so-called 'concurrent' instruments. In the present study, ESM measures will be compared to scores obtained from SR-BDs and symptom questionnaires. Since ESM data have a hierarchical structure, with repeated measurements (level 1) nested within subjects (level 2), these analyses will be performed using linear mixed-effects models, including a random intercept and an autoregressive (AR1) covariate structure. ^{62,63}.
- To quantify the difference of scores between the two methods (ESM and SR-BD), a delta score is calculated. Using the same multilevel analysis, thus adjusting for clustering within patients and for correlations between repeated

measures, we will test whether this delta score is different from 0. In like manner, the differences between SR-BD scores and ESM maximum scores of the day will be tested.

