6.2 Other study parameters

- Baseline characteristics / descriptives will be described as means and standard deviations (in case of normal distribution) or medians and interquartile ranges (in absence of a normal distribution) for continuous variables and frequencies for categorical variables. The following patient characteristics will be investigated: gender, age, race, length, weight, highest level of education, work status, smoking, alcohol use, drug use, caffeine use and medication.
 - To investigate if certain patient characteristics lead to a different retrospective perception of urgency, possible predictors of a larger deltascore (i.e. the differences in urgency reporting between ESM day-mean scores and the end-of-day SR-BD scores) will be tested: i.e. gender, age, presence of comorbid panic disorder, psychological symptoms (HADS).

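### Diary mean against ESM maximum cannot, by itself, show whether a per-void diary reports the daily peak of urgency, and the diary score in the delta is defined in two ways

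*Combined protocol and SAP*

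**What the plan says.** Section 1 (Part I, objective 1) adds to the correlation and mean-urgency hypotheses the expectation that "in the SR-BDs the daily peak of urgency scores is reported rather than the average level of urgency over the day".

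Section 4.2.3 describes the diary as a per-void record: "The SR-BD has to be filled out after each micturition", and "these diaries also include the degree of urge and the perception of bladder fullness during each void". Section 4.1.1 gives it a recall period of several minutes. No daily rating is described in any of these places.

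Section 6 (Part I) plans two comparisons of level. One sets ESM day-means against diary day-means, "to test whether average symptom scores of the day reflect the day-mean SR-BD scores", and also forms a delta score from the two methods. The other uses the peak: "In like manner, the differences between the mean SR-BD scores and ESM maximum scores of the day will be tested". Section 6.1 repeats the second without naming the diary summary: "the differences between SR-BD scores and ESM maximum scores of the day will be tested". For the delta, section 6.1 says "we will test whether this delta score is different from 0". No equivalence margin is given, and no analysis uses the diary maximum.

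Section 6.2 defines the urgency delta from "ESM day-mean scores and the end-of-day SR-BD scores", while section 6 defines the same delta from day-means of both instruments.

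**The concern.** Peak reporting is easy to define for a diary with one recalled score per day: the patient is asked about the day and answers with its worst moment. A per-void diary asks no such question. Its day-mean is computed by the analyst from several ratings, high and low alike. The plan does not say what reporting the peak would then mean.

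The contrast used is a mean against a maximum. The two differ even when both instruments measure the same thing. They can also coincide for a reason unrelated to reporting, because diary ratings are made at voids, when urgency may be high, while beeps fall at random times. Following section 6 as written could therefore credit or deny the standard diary a reporting tendency that the data do not identify. Urgency on these two instruments is the Part I main endpoint, so the interpretation matters.

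**Working it through.** The plan gives no figure for this contrast, so there is none to reproduce.

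**Inputs from the protocol.** Ten random beeps a day between 07:00 and 22:00 (section 4.2). At least 6 of 10 answered counts as compliant (section 6.1). Three days carry both instruments (section 4.2). The ESM scale has 11 points (section 6.1). The diary's urgency scale is not given.

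**Assumptions, not in the protocol.** Both scales run 0-10. The urgency patterns are as stated in each step.

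**1. Both tools rate the same process.** For k independent normal ratings, the expected maximum exceeds the mean by 1.27 SD (k = 6) or 1.54 SD (k = 10). With SD 2:

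- k = 6: 1.27 × 2 = 2.5 points
- k = 10: 1.54 × 2 = 3.1 points

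Simulation used ratings rounded and clipped to 0-10, mean 3, SD 2, lag-1 correlation 0 to 0.5 and 10 diary ratings. Diary mean minus ESM maximum was -2.1 to -2.5 with 6 beeps and -2.7 to -3.0 with 10. Mean minus mean was 0. There is no method difference here, yet the contrast is clearly negative.

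**2. Urgency builds up to each void and every void is rated accurately.** A case that can be checked by hand: urgency rises linearly from 0 to the same value p before every void.

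- Diary mean = p
- A random beep is uniform on 0 to p, so the expected ESM maximum of k beeps = p × k/(k + 1)
- Diary mean minus ESM maximum = p/(k + 1)

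With p = 6 this is 6/7 = 0.86 for 6 beeps and 6/11 = 0.55 for 10. The diary mean lies close to the ESM maximum with no reporting error. Since all voids are alike, accurate ratings and peak ratings give identical data in this case.

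**3. Simulation with varying voids** (50 patients, 3 days, about 9 voids a day, 5 to 10 answered beeps):

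| What the patient does | Diary mean minus ESM maximum | Diary mean minus ESM mean |
|---|---|---|
| Rates each void accurately | about -2.6 to +2.1 | about +1.0 to +4.7 |
| Rates every void at the day's peak | about +1.7 to +4.3 | not needed here |
| Rates every void at the day's average | about -2.9 to -4.3 | about 0 |

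- Full peak reporting did not give the near-zero result that would be read as support.
- In one accurate-rating pattern the contrast went from +0.46 (5 beeps) to +0.21 (6), -0.14 (8) and -0.40 (10) through response rate alone.
- In some accurate-rating patterns the contrast was negative while the diary maximum matched the true peak (for example contrast -2.18, diary maximum 8.49, true peak 8.50). A negative contrast alone therefore does not refute the hypothesis.

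**4. Maximum against maximum.** Under accurate ratings with build-up, diary maximum minus ESM maximum was about +2.0 to +4.5, because random beeps miss the urgency present at voiding. Under step 1 it was about 0 with 10 beeps and about +0.5 to +0.6 with 6.

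**5. Section 6.2 beside sections 4.2.3 and 6.** An end-of-day diary score and a day-mean of per-void ratings are different quantities. The same delta is defined with each.

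**The case against.** The strongest reply is that section 6 supplies two contrasts and they can be read together. A diary mean near the ESM mean and far below the ESM maximum would count against peak reporting. This stands. A reader might infer that no result could ever bear on the hypothesis, but the planned mean-against-mean test rules that out. It does not rescue the other direction: a diary mean well above the ESM mean and near the ESM maximum is what the hypothesis predicts, and also what accurate ratings at voids produce.

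A second reply is that section 1 does not call peak reporting a recall error. If void ratings simply cluster near the day's peak, the statement could be a fair description. That is a possible reading, and it shows why the quantity must be defined.

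Third, comparing maximum with maximum is not a clean replacement. Step 4 confirms this.

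Fourth, neither section 6 nor section 6.1 says that the contrast serves the peak expectation. The link is inferred, although no other analysis addresses that expectation.

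Finally, the diary form itself is not in the document. A reader might infer that an end-of-day rating definitely does not exist. The text supports only that sections 4.1.1 and 4.2.3 describe none while section 6.2 refers to one. If one is collected, the argument changes.

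**Conclusion.** The concern holds in limited form. Mean diary score minus ESM daily maximum, tested against zero, cannot alone distinguish peak reporting from accurate ratings made at voids. It is uninformative over a wide range of results, not over all of them. A non-significant result would not establish equality either, since no margin is set, and the ESM maximum shifts with the number of answered beeps.

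A reader might go further and treat the Part I conclusion as an artefact. The document does not support that: the peak statement is an added expectation, and the correlation and mean-urgency hypotheses do not use the maximum.

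The conflict between sections 6 and 6.2 over the diary score stands on the text alone. The simulated sizes are illustrative. They rest on assumed urgency patterns and on a 0-10 scale for both tools.

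**What to change.** - **Section 1:** drop the peak expectation, or restate it as a defined quantity for a diary completed at each void.
- **Sections 6 and 6.1:** do not use mean against maximum as a test of peak reporting. Keep the planned mean-against-mean comparison. In section 6.1, name the diary summary used.
- **If a peak comparison is kept:** report diary day-maximum against ESM day-maximum as a descriptive supplement only, accounting for the number of answered beeps and stating that random beeps miss urgency at voiding. Alternatively, pair each void rating with the nearest beep.
- **Section 6.2:** reconcile the end-of-day diary score with sections 4.2.3 and 6, so that the delta has one definition.

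The cost is wording in sections 1, 6, 6.1 and 6.2. The diary day-maximum comes from ratings already collected. Pairing would need a rule for the time window. The downside is that the peak-reporting hypothesis is given up or weakened.

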6.1 Primary study parameter

Data used for analysis will comprise patient-reported scores from ESM, paper SR-BDs and single-time paper symptom questionnaires. The PROM will be psychometrically evaluated with regard to validity and reliability. These parameters will characterize the ESM measure and allow insight into the potential role of this method in clinical practice. Validity and reliability will be assessed according to following components ^{29,62,63}:

- Content validity reflects the extent to which the instrument as a whole measures all the relevant aspects that are indicative to the specific condition and population. This can be determined by taking into account evidence from qualitative studies, performing cognitive interviews to evaluate patients' understanding with the instrument and by taking into account experts' opinions ^{62,63}. In this study, content validity is assured by basing ESM items on theoretical constructs from the literature as well as by performing patient focus groups and expert meetings.
- Concurrent validity reflects the correlation between a new test and an existing test that purport to measure the same construct. ESM scores will be correlated with scores of so-called 'concurrent' instruments. In the present study, ESM measures will be compared to scores obtained from SR-BDs and symptom questionnaires. Since ESM data have a hierarchical structure, with repeated measurements (level 1) nested within subjects (level 2), these analyses will be performed using linear mixed-effects models, including a random intercept and an autoregressive (AR1) covariate structure. ^{62,63}.
- To quantify the difference of scores between the two methods (ESM and SR-BD), a delta score is calculated. Using the same multilevel analysis, thus adjusting for clustering within patients and for correlations between repeated

measures, we will test whether this delta score is different from 0. In like manner, the differences between SR-BD scores and ESM maximum scores of the day will be tested.

- Internal consistency is a reliability measure to analyse correlations between single items of an instrument/scale that are supposed to measure similar symptoms or domains. The homogeneity of a scale (*e.g.* internal consistency) is analysed by Cronbach's α-statistic. A coefficient of at least 0.6 is generally considered as acceptable, values above 0.8 are considered as good to very good ^{29,64-66}. As subjects are usually not able to respond after every beep (for example because of driving a car), completion of ≥6 of the 10 beep-questionnaires per day will be considered as being compliant. Not completed beep-questionnaires will be considered as missing values in the analyses.^{1,67}
- Test-retest reliability reflects the consistency between repeated measurements of the same outcome in the same test conditions, but at different times. We will ascertain on individual response consistency over the study period. Scores of the first half-week will be correlated with scores of the second half-week. A test-retest reliability coefficient of more than 0.70 will be considered adequate ²⁹.
- Differences between OAB symptom scores assessed by the OAB-q / ICIQ-FLUTS / IPSS and ESM could only be analysed on subject level, by paired sample t-test, due to lack of intra-subject variation in the OAB-q scores (only one measurement per subject). Scoring scales of the retrospective questionnaires and ESM will be harmonized by rescaling the ESM data from a 11-point to a 6-point and 5-point scale. In order to assess whether the rescaling affected the reliability of urological symptom related questions in ESM, a Cronbach's a was calculated for the original and rescaled data. Subject-means (i.e. means over 7 days) of ESM data were calculated and compared to the corresponding OABg / ICIQ-FLUTS /IPSS scores.
- Following the COSMIN guidelines it should be aimed to assess the responsiveness of the ESM tool too. However, since responsiveness is the sensitivity of an instrument to detect difference between two points in time within groups⁶⁸, this psychometric property, it is not meaningful to assess this, since the ESM measures repeatedly over a longer period of time (10 times a day for 7 days). It is expected that there will be a fluctuation of symptoms during the assessment period, however 'big' differences that could be assessed with statistical analysis are not expected to occur. The

aim of this study is not to detect change between two groups with the use of statistical analysis. It is rather to evaluate symptom pattern recognition of the ESM tool. Therefore responsiveness will not be assessed as psychometric property in this study.

A significance level (α) of 0.05 will be considered statistically significant. Data analysis will be performed using IBM SPSS Statistics software version 23.0 (IBM Statistics for Windows, Armonk, New York).

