4.2 Study procedures

Participants will accomplish the Experience Sampling Method for seven consecutive days during their regular daily life. Previous ESM validation studies validated for the use of the ESM for seven days too.⁴³

During the last three consecutive days of the ESM, patients will also keep a SR-BD following the standard of care. A 7-day voiding diary is a reliable and valid method for documenting the change in symptoms of overactive bladder in men and women with predominantly urge incontinence. However, 3-day voiding diaries are as accurate as the 7-day diary, but patient burden is reduced. Therefore, a 3-day sensation-related bladder diary is used in the standard of care of the department of Urology of MUMC+, Zuyderland Heerlen/Sittard and University Hospital Antwerp.^{46,47} Furthermore, during the first four days of the study, ESM outcomes are not influenced by outcomes reported with the sensation-related bladder diaries. This is in alignment with previous studies.^{4,43}

On the last day of the study period, participants will fill out the several retrospective symptom questionnaires.

To accomplish the ESM, they need to carry their own smartphone or (in case they do not have one) another digital device, which will be lent to them for this period. On the smartphone or digital device an application, specifically developed for this project, will be downloaded. This application will run the PROM as follows.

The concerning device will send out an auditory signal 10 times a day at random moments between 07:00 am and 22:00 pm. During 10 minutes following the signal participants can complete a questionnaire, *i.e.* the developed PROM, on the device (see F1. 'ESM_Vragenlijst_Versie 1.0 (11.08.2017)'). After these 10 minutes the questionnaire will not be available until the next beep and is considered missing data. Therefore, subjects are instructed to complete as many questionnaires as possible each day, as soon as possible following each beep, but to pass over questionnaires when completing is impossible. For example, subjects should not fill out questions when driving a car. The questions will be identical between the different moments during the day.

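### Concurrent validity is to be read as a correlation against 0.4 and 0.8, but the analyses assigned to it return a regression slope and a paired t-test, not a correlation

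*Combined protocol and SAP*

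**What the plan says.** Section 1 (Objectives) gives the same interpretation under Part I objective 1 and Part II objective 2. "Correlation coefficients between 0.4 and 0.8 are considered appropriate"; a lower value suggests that the ePRO measures another construct; above 0.8, "there is no rational for replacing the conventional methods by the new (more intensive) method". It adds: "For each correlation coefficient its significance will be checked as well".

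Section 6.1, under concurrent validity, says "ESM scores will be correlated with scores of so-called" concurrent instruments, names both the SR-BDs and the symptom questionnaires, and then states that "these analyses will be performed using linear mixed-effects models, including a random intercept and an autoregressive (AR1) covariate structure".

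Section 6, Part I, defines the diary model. "Currently the SR-BD can be seen as the standard method and will therefore be used as dependent variable in the analysis", and "ESM day-mean scores of individual symptoms will be used as predictor". It mentions no centring or standardisation. The two instruments overlap on three days only (section 4.2): "During the last three consecutive days of the ESM, patients will also keep a SR-BD".

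For the single-time questionnaires, section 6.1 plans a subject-level paired t-test against the 7-day ESM mean, after rescaling the ESM scores. It specifies no correlation beside that test.

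**The concern.** The criterion and the method do not meet. The criterion is a correlation, which is unit-free and bounded by 1. The diary model returns a slope, which depends on the ratio of the two SDs and is not bounded by 1. With an uncentred day-mean as predictor, it also blends two associations: whether patients with higher ESM scores have higher diary scores, and whether a patient's worse ESM days are also worse diary days. For the questionnaires, a paired t-test compares means and says nothing about correlation.

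Someone must therefore decide after data collection which number is held against 0.4 and 0.8. For the diary the candidates are the slope, a correlation pooled over days, a correlation of subject means, and a within-patient correlation. The Objectives attach very different readings to the two ends of the scale, so the choice could change what is reported about ESM as a replacement for current tools.

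**Working it through.** **1. The plan's own figure.** Section 3.4 wants 50 evaluable patients with 23% non-valid data: 50 / 0.77 = 64.9, so 65; with the 23.2% also cited there, 50 / 0.768 = 65.1, so 66. The stated 66 is reproduced. It leaves 66 × 0.77 = 50.8 patients, or 33 × 0.77 = 25.4 per sex. This number rests on a rule of thumb, not on a correlation, so the present point does not affect it.

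**2. Criterion against method.**

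| Comparator | Criterion (section 1) | Analysis (sections 6, 6.1) | Yields a correlation? |
|---|---|---|---|
| SR-BD | r against 0.4 and 0.8 | Random-intercept/AR1 model, diary on ESM day-mean | No: unstandardised slope |
| Questionnaires | r against 0.4 and 0.8 | Paired t-test on subject means | No: mean difference |

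**3. Does the level matter?** Assumptions (the documents give none of these values): 50 patients, 3 shared days, between-patient SD 1.5 and within-patient SD 1.0 for both instruments. Write rb and rw for the between- and within-patient correlations.

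- Pooled r = (2.25 rb + rw) / 3.25
- Subject-mean r = (2.25 rb + rw/3) / (2.25 + 1/3)
- Slope: median of 400 simulated random-intercept REML fits

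For rb = 0.7 and rw = 0.3, pooled r = (1.575 + 0.3) / 3.25 = 0.58 and subject-mean r = (1.575 + 0.1) / 2.583 = 0.65.

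| rb / rw | Subject-mean r | Pooled r | Slope | Within-patient r |
|---|---|---|---|---|
| 0.6 / 0.6 | 0.60 | 0.60 | 0.60 | 0.60 |
| 0.7 / 0.3 | 0.65 | 0.58 | 0.45 | 0.30 |
| 0.2 / 0.9 (extreme) | 0.29 | 0.42 | 0.86 | 0.90 |

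Adding AR1 changes the slope little (0.44 and 0.86 in the last two rows).

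**4. Does the scale matter?** If both levels share the same r, slope = r × (SD of SR-BD / SD of ESM). With r = 0.6 the slope is below 0.4 when the ratio is under 0.4 / 0.6 = 0.67, and above 0.8 when it exceeds 0.8 / 0.6 = 1.33. A ratio of 0.5 gives 0.30 and a ratio of 1.5 gives 0.90, although the true correlation is in band both times.

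**5. Does the significance check settle it?** No. At n = 50 and two-sided 0.05, any r of at least 0.279 is significant, including values that the plan calls very weak.

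**6. Precision once r is named.** Fisher z for r = 0.6: atanh(0.6) = 0.693.

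- n = 50: 0.693 ± 1.96/√47 = 0.407 to 0.979, so r from 0.39 to 0.75.
- n = 25: 0.693 ± 1.96/√22 = 0.275 to 1.111, so r from 0.27 to 0.80.

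**The case against.** Much can be said for the plan. The bands are worded as hypotheses, and no go/no-go step, sample size or clinical action hangs on them. The Objectives equate concurrent instruments with retrospective questionnaires; each of these is completed once, so any correlation with ESM can only be at subject level. Pooled and within-patient values do not arise there, and what stays open is mainly Pearson or Spearman. For the diary, section 6 already fixes outcome, predictor, day-mean unit and covariance structure. The delta scores subtract one instrument from the other, which presupposes comparable scales. In the 0.7/0.3 case the subject-mean r, pooled r and slope all stay in band.

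These arguments limit the consequences but do not close the gap. Section 6.1 lists SR-BDs under concurrent validity and section 4.1.1 calls them retrospective, so the bands extend to them. A fixed subject level for the questionnaires is still not a planned correlation. Comparable scale ranges do not ensure equal SDs. Standardising both scores would not settle the level either: with rb = 0.8 and rw = 0.3, the standardised slope is about 0.50, against 0.73 for subject means and 0.30 within patients.

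A reader might infer from the 0.2/0.9 row that the study's conclusion is likely to flip. The documents do not support that: nothing in them suggests so wide a gap between levels. Nor do they show that the SDs of the two instruments differ.

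**Conclusion.** The point holds: as written, no planned analysis produces the coefficient that the Objectives say will be read against 0.4 and 0.8. This is certain from the text. How much it changes the reading is not, because it rests on assumed SDs and correlations. The effect ranges from none (0.6 at both levels, equal SDs), through a split that affects only the within-patient value (0.7/0.3), to a wrong band for the slope when the SD ratio lies outside 0.67 to 1.33 with r = 0.6.

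A reader might go further and conclude that the mixed model or the paired t-test is invalid. That does not follow. The model is a sound test of association and the t-test answers its own question about differences. The delta-score tests and the expectations on mean and peak urgency are untouched. The gap should be closed before analysis; it does not endanger the data.

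**What to change.** Keep the mixed model as the test of association, and add the following.

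- **SR-BD (section 6, Part I, and concurrent validity in section 6.1).** State that the quantity read against 0.4 and 0.8 is the correlation of subject means over the three shared diary days, with a 95% CI and the bands applied to the point estimate. Label it as such: three-day means still carry some within-patient covariance (a true between-patient value of 0.2 with 0.9 within patients reads 0.29, or 0.46 at a between/within SD ratio of 0.75). If a pure between-patient value is wanted, take it from a bivariate two-level model. Report the within-patient correlation beside it in either case.
- **Questionnaires (section 6.1).** Beside the paired t-test, add the subject-level correlation of the 7-day ESM mean with each questionnaire score, with a 95% CI. Say whether it is Pearson or Spearman.

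A correlation does not change under linear rescaling, so this works whatever scale the diary uses. The cost is a few sentences and slightly more analysis on the same data, with no added patient burden. The downside is visibly wide intervals: for r = 0.6, 0.39 to 0.75 at n = 50, and 0.27 to 0.80 for the sex-specific questionnaires at about 25 per sex.
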